4.7.1.3 Multiple Comparisons/Multiplicity

No adjustment for multiple comparisons is planned for the efficacy endpoints being monitored.

Safety results, including the summaries of AEs and changes in laboratory and vital signs data, will be interpreted on clinical grounds. No formal statistical hypothesis testing will be performed.

4.7.1.4 Interim Analyses

No interim analysis is planned for this study.

4.7.1.5 Examination of Subgroups

To assess the effects of various demographic and baseline characteristics on treatment outcome, subgroup analyses for the primary endpoint, ADAScog-11, will be performed based on the following variables:

- [REDACTED]
- [REDACTED]
- [REDACTED]
- [REDACTED]
- [REDACTED]
- [REDACTED]
- [REDACTED]
- [REDACTED]
- [REDACTED]
- [REDACTED]
- [REDACTED]
- [REDACTED]
- [REDACTED]
- [REDACTED]

- [REDACTED]
- [REDACTED]
- [REDACTED]
- [REDACTED]
- [REDACTED]

[REDACTED]

[REDACTED]

- [REDACTED]
- [REDACTED]
- [REDACTED]
- [REDACTED]
- [REDACTED]

[REDACTED]

- [REDACTED]
- [REDACTED]

[REDACTED]

- [REDACTED]
- [REDACTED]

[Redacted]

- [Redacted]
- [Redacted]

[Redacted]

- [Redacted]
- [Redacted]
- [Redacted]
- [Redacted]
- [Redacted]
- [Redacted]
- [Redacted]

[Redacted]

[REDACTED]

4.7.1.6 Exploratory Analysis of the Primary Endpoint

To test the overall efficacy of SUVN-502 over placebo regardless of dose, an exploratory analysis on the change from Baseline in ADAScog-11 score will be performed comparing placebo to the combined SUVN-502 treatment groups. This analysis will use the same methods as the primary efficacy analysis but the 50 mg and 100 mg SUVN-502 dose levels will be combined into one treatment group.

4.7.2 Primary Efficacy Endpoint- – ADAScog-11

The primary endpoint for the assessment of efficacy is the change from Baseline to Week-26 in the ADAScog-11 score.

The ADAScog-11 is a brief measure of cognition, including word recall, commands, constructional praxis, naming objects and fingers, ideational praxis, orientation, word recognition, remembering test instructions, spoken language ability, word-finding difficulty, and comprehension of spoken language.

Word Recall

The score for this item is the mean number of words not recalled on the three trials, for a maximum score of 10.

Commands

The score for this item is based on the total number of commands performed incorrectly, where the maximum score is 5. Scoring is summarized in the chart below:

0	= all commands correct
1	= 1 command incorrect
2	= 2 commands incorrect
3	= 3 commands incorrect
4	= 4 commands incorrect
5	= 5 commands incorrect

Constructional Praxis

The score for this item is based on the total number of forms drawn incorrectly, where the maximum score is 5. Scoring is summarized in the chart below:

0	= all 4 drawings correct
1	= 1 form drawn incorrectly
2	= 2 forms drawn incorrectly
3	= 3 forms drawn incorrectly
4	= 4 forms drawn incorrectly
5	= no figures drawn

Naming Objects and Fingers

The score for this item is based on the number of different objects and fingers that the subject named incorrectly. The maximum score for this item is 5 and is summarized in the chart below:

0	= 0-2 items (objects and fingers) named incorrectly
1	= 3-5 items (objects and fingers) named incorrectly

2	= 6-8 items (objects and fingers) named incorrectly
3	= 9-11 items (objects and fingers) named incorrectly
4	= 12-14 items (objects and fingers) named incorrectly
5	= 15-17 items (objects and fingers) named incorrectly

Ideational Praxis

The score for this item is based on the total number of components the subjects are not able to perform. The maximum score is 5. Scoring is summarized in the chart below:

0	= all components performed correctly
1	= failure to perform 1 component
2	= failure to perform 2 components
3	= failure to perform 3 components
4	= failure to perform 4 components
5	= failure to perform 5 components

Orientation

The score for this item is based on the total number of responses incorrect. The maximum score is eight. Scoring is summarized in the chart below:

0	= all responses correct
1	=1 response incorrect
2	=2 responses incorrect
3	=3 responses incorrect
4	=4 responses incorrect

5	=5 responses incorrect
6	=6 responses incorrect
7	=7 responses incorrect
8	=8 responses incorrect

Word Recognition

The score for this item is the total number of words not recalled. The maximum score for this item is 12.

Remembering the Instructions

The score for this item is based solely on the subject’s performance on the Word Recognition Task. The score corresponds to the number of reminders given after the first two rounds only reminders after the second word are included in the scoring range of 0-22. Scoring for this item is summarized below, with a maximum score of 5.

0	None	= subject never needs extra reminders of instructions
1	Very mild	= forgets once
2	Mild	= must be reminded 2 times
3	Moderate	= must be reminded 3 or 4 times
4	Moderately severe	= must be reminded 5 or 6 times
5	Severe	= must be reminded 7 or more times

Comprehension

The score for this item is based on the evaluation of the subject’s ability to understand speech (what is being said to them). Scoring is summarized in the chart below.

0	None	= subject understands
---	------	-----------------------

1	Very mild	= one or two instances of misunderstanding
2	Mild	= 3-5 instances of misunderstanding
3	Moderate	= requiring several repetitions and rephrasing
4	Moderately severe	= subject only occasionally responds correctly; i.e. yes/no questions
5	Severe	= subject rarely responds to questions appropriately, not due to poverty of speech

Word Finding Difficulty

The score for this item is based on rating impairment in expressive language (difficulty in finding the desired word in spontaneous speech). The maximum score is 5. Scoring is summarized in the chart below:

0	None	= subject speaks clearly and/or is understandable
1	Very mild	= 1 instance of lack of understandability
2	Mild	= subject has difficulty less than 25% of the time
3	Moderate	= subject has difficulty 25-50% of the time
4	Moderately severe	= subject has difficulty more than 50% of the time
5	Severe	= one or two word utterance; fluent, but empty speech; mute

Spoken Language Ability

The score for this item is a global rating of the quality of the subject's verbal communication. The score range is 0-5, as summarized in the chart below.

0	None	= subject speaks clearly and/or is understandable
1	Very mild	= 1 instance of lack of understandability

2	Mild	= subject has difficulty less than 25% of the time
3	Moderate	= subject has difficulty 25-50% of the time
4	Moderately severe	= subject has difficulty more than 50% of the time
5	Severe	= one or two word utterance; fluent, but empty speech; mute

The total score for the ADAScog-11 is the sum of the above 11 items. The maximum score is 70 points. A lower score indicates a better performance.

If any item is not administered because the subject is too cognitively impaired to complete, then the subjects receives the maximum amount of points for that item. Any other reason for not administering the item on the eCRF will be left as missing. Handling of missing items in the ADAScog-11 is summarized in [Section 4.7.1.2](#).

Summary

ADAScog-11 scores will be summarized by treatment group and visit in terms of absolute values and changes from baseline, both for the observed case and LOCF analyses.

A listing of observed and change from Baseline value will be provided.

Analysis

A MMRM will be used to test the hypotheses stated in [Section 4.7.1](#) that there is no difference between SUVN-502 and placebo in the mean change from baseline at Week 26 for the ADAScog-11 score. The LS means of each treatment group, and the differences between each SUVN-502 dose group and placebo will be reported for Weeks 4, 13, and 26, along with the corresponding 95% confidence intervals and p-values.

The change from baseline score at each scheduled post-baseline visit (according to the Study Schedule) during the treatment period will be the dependent variable. The model will include the fixed effects of treatment, week, treatment-by-week interaction, and APO-E status (carrier- one allele, carrier- two alleles, and non-carrier), as well as a continuous covariates of baseline score, the baseline score-by-week interaction, age, and Baseline MMSE score. Pooled site, as defined in [Section 4.2.4](#), will be included as a random effect. Week will be considered a categorical variable with values equal to the visit numbers at which the scales were assessed. An unstructured covariance matrix will

initially be used to model the within-subject variance-covariance errors. The following SAS code will be used to perform the analyses:

```
PROC MIXED;  
CLASS treat week subjid apoe site;  
MODEL outcome = treat week treat*week base base*week apoe mmse_base age /  
          DDFM=kr;  
RANDOM site;  
REPEATED week / SUBJECT=subjid TYPE=UN;  
LSMEANS treat/ cl diff;  
RUN;
```

If the unstructured covariance structure matrix results in a lack of convergence, the following covariance structures will be used in sequence: heterogeneous compound symmetry covariance structure and compound symmetry covariance structure, until the model converges. The Kenward-Roger approximation will be used to estimate the denominator degrees of freedom.

A plot showing the LS mean change from baseline in ADAScog-11 over time within each treatment group will be provided.

Sensitivity analyses to investigate the impact of the choice of method for handling missing data and the choice of analysis population will be performed as described in [Section 4.7.1.2](#).

The homogeneity of the treatment effect for a number of important subgroups will be investigated as described in [Section 4.7.1.5](#).

The combined treatment effect of SUVN-502 regardless of dose will be investigated as described in [Section 4.7.1.6](#).

Additional ADAScog-11 analyses will be performed on subsets of the mITT Population and EP:

- [REDACTED]
- [REDACTED]
- [REDACTED]

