11 APPENDICES

**APPENDIX 1:
ALZHEIMER’S DISEASE ASSESSMENT SCALE - COGNITIVE BEHAVIOR
(ADAS-Cog)**

Used with permission from the NIA Alzheimer’s Disease Cooperative Study

ADAS Initial Conversation Notes

Instructions:

For specific instructions for all tasks, refer to the Administration Manual. The first several minutes are spent in open-ended conversation in order to assess various aspects of expressive and receptive speech. Then the remaining cognitive tests are administered. Language abilities are evaluated throughout the interview and on specific tests. Questions eliciting “yes” and “no” answers assess comprehension on a very basic level. Other questions should require specific information and well-developed communication skills. Engage the subject in a short conversation about neutral topics (for example: weather, the subject’s trip to the clinic, or what the subject had for breakfast). This conversation will help to put the subject at ease before the testing begins and will give the examiner an opportunity to observe how well the subject can use and understand language. There are three clinical ratings of language ability on the cognitive part of the ADAS. Use this page to record your interview notes. Documentation should be evident on this form to support rating of spoken language ability, word finding difficulty and comprehension. Any rating of impairment should be supported by notes documented on this page.

Possible Topics:	Weather	Breakfast	Clinic trip	Other
1) Comprehension				
2) Word finding				
3) Spoken language				
Testing Comments:				

1. WORD RECALL TASK (Word List 1):

To begin testing, say: **“I am going to show you some words printed on these white cards. Please read each word out loud and try to remember it, because later I will ask you to try to remember all of the words I have shown you. Ready, read the word and try to remember it.”**

Present each word to the subject and ask him/her to say it aloud. After all 10 words have been presented, say: **“Good, now tell me all the words you can remember that were on that list.”** Prompt with **“Any others?”** as necessary. For trials 2 and 3 say: **“Now I am going to show you that same list again. Read each word out loud and try to remember it.”** *Examiner should check a response (yes/no) for every word.*

Trial 1	Word recalled correctly?	
	Yes	No
Butter		
Arm		
Shore		
Letter		
Queen		
Cabin		
Pole		
Ticket		
Grass		
Engine		
Total Not Recalled		

Trial 2	Word recalled correctly?	

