- Subject unable for physical reasons
- Subject unable for cognitive reasons (if selected, circle “8” on the scoring table below)

Scoring: (circle one)	
0	= all responses correct
1	= 1 response incorrect
2	= 2 responses incorrect
3	= 3 responses incorrect
4	= 4 responses incorrect
5	= 5 responses incorrect
6	= 6 responses incorrect
7	= 7 responses incorrect
8	= 8 responses incorrect

7. WORD RECOGNITION TASK (Word List 1):

In the learning portion of this test, the subject is given one trial to learn a list of 12 words. Say: **“I am going to show you some words printed on these white cards. I want you to read each word out loud and try to remember it.”**

In the recognition portion of this test, the examiner should say: **“Now I’m going to show you another set of words. Some of the words were on the list I just showed you and others are new. For each word I want you to tell me whether it is one of the words I just showed you.”**

The examiner shows the first word and says either **“Is this one of the words I showed you before, yes or no?”**, or **“Did I show you this word before?”** The same instruction is given before the second test word. For the remaining test words the examiner should say: **“How about this one?”**

Check the **subject’s response** to each word **Yes** or **No**. If the subject needs to be reminded of the task during the exam, the examiner should repeat the question and place a check in the reminder column.

If task not administered, please specify reason (check one):

- Not done (for reasons other than physical/cognitive impairment)
- Subject refused
- Subject unable for physical reasons
- Subject unable for cognitive reasons (**Enter maximum score of “12”**)

Word	Check Subject Response		
	Yes	No	*R
Nurse			
Magazine			
Wizard			
Van			
Leopard			
Sale			
Sea			
Train			
Coin			
Ship			
Institution			
Map			
Axe			
Board			
Carrot			
Milk			
Volume			
Forrest			
Anchor			
Gem			
Cat			
Fund			
Edge			
Cake			
Total Not Recalled: (Maximum score = 12)			

*Reminder given

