4.7.1.2 Handling of Dropouts or Missing Data

For the primary efficacy analyses missing total scores will be maintained as missing. Under the MMRM model, missing data is assumed to be missing at random. However, sensitivity analyses to assess the impact of missing data will also be conducted. These analyses will utilize the same method as described for the primary and secondary endpoints, however, missing total scores will be imputed using the z-score Last Observation Carried Forward (zLOCF) approach prior to analysis. That is, the missing value will be imputed as the score that is the same number of standard deviations from the treatment group mean at that time point as at the subject's last observed value. The missing values will be imputed using this method. Then the imputed values will be recalculated using the newly imputed data in the calculation of the treatment group means. The value that is the same number of standard deviations from that treatment group mean will be used in the analysis. It is noted that the zLOCF approach is unbiased when dropouts are missing at random within the treatment groups or missing at random after taking into account the severity at the time of dropout.

If the proportion and/or pattern of missing data is found to be different to that expected, additional sensitivity analyses may be required. These will be documented in the CSR.

Handling of Missing Items in Calculating Totals

All total and subscale scores for efficacy will be derived from individual items. If any of the individual items are missing or unknown, every effort will be made to obtain the score for the missing item or items. If individual items that derive the total score are missing and fit the below criteria, then the remaining non-missing items will be used to impute the total score. This imputation is independent of the sensitivity analysis described at the beginning of this section and will be used for the primary and secondary analyses.

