For the ADAScog-11, if less than 30% (fewer than 21 points) of the total score is missing, the total score (maximum 70) will be imputed using the available non-missing data. If the missing item is available at previous visits, then the missing data will first be imputed using straight line imputation. That is, a simple regression line will be fitted to interpolate or extrapolate the missing item. If the extrapolated value is outside of the range of the item, then the value will be cut off at the maximum/minimum value and will be used in the calculation of the total score. If there are items that have no non-missing values for that subject, then the total remaining items will be multiplied by a factor that includes the maximum score for the missing items. For example, if the first item, "Word Recall Task," which ranges from a score of 0 to 10 (maximum=10) is missing, and the second item "Commands," which ranges from a score of 0 to 5 (maximum=5) is missing, then the multiplication factor= $70/(70-[10+5])=70/55=1.27$. Thus, the total score for this example is the sum of the remaining 9 items multiplied by 1.27. The imputed number will be rounded up to the nearest integer. Specifically, if the sum of the items not including the missing "Word Recall Task" and "Commands," is 50, then the imputed score is $50*1.27=63.5$. So, the imputed total score for this subject, would be 64. If more than 30% of the total score is missing, the total score for the ADAScog-11 at that visit will be considered missing.

The same approach will be used for missing items in the ADCS-ADL and CDR-SB. The only exception is that the imputed total score for CDR-SB will not be rounded up to the nearest integer.

For all other scales, if any item is missing, any total or sum involving that item will be considered missing. This includes MMSE, NPI, and C-SDD.

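### SAP 4.7.1.2 rounds only imputed totals up and draws a line through too few visits for missing ADAScog-11 items, although the SAP holds better alternatives

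*SAP*

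**What the plan says.** SAP 4.7.1.2 states that "All total and subscale scores for efficacy will be derived from individual items". When less than 30% of the ADAScog-11 is missing (fewer than 21 of 70 points), the total is imputed in two steps.

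- **Line.** "If the missing item is available at previous visits, then the missing data will first be imputed using straight line imputation". The regression line may interpolate or extrapolate, and a value outside the item's range is cut to the limit. The SAP gives no minimum number of values, no list of visits in the fit and no time axis.
- **Proration.** This applies only to an item for which the subject has no value at any visit. The sum of the other items is multiplied by 70/(70 − m), where m is the missing maximum. The result goes up to a whole number; the worked example turns 50 into 63.5 and then 64.

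ADCS-ADL and CDR-SB follow the same approach, except that imputed CDR-SB totals are not rounded. SAP 4.2.1 defines baseline as the latest valid assessment before dosing. Under SAP 4.7.2, an item not given because of cognitive impairment scores its maximum, and any other reason leaves it missing.

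Two item definitions in SAP 4.7.2 also matter. For Word Recognition, "The score for this item is the total number of words not recalled. The maximum score for this item is 12". The Word Finding chart has the same anchors as the Spoken Language chart, whereas protocol Appendix 1 item 10 has different ones.

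**The concern.** These rules fix the value of the primary endpoint wherever an item is missing, and the SAP contains a sounder option in each case.

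Rounding is applied to imputed totals only. Observed totals have no rounding rule and can fall on thirds, because Word Recall is a mean of three trials. Taking imputed totals up makes ADAScog-11 look worse (lower is better) and ADCS-ADL look better (lower is more impaired), so the same rule pushes two scales in opposite clinical directions.

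The line rule can rest on two points close together in time and be read off six months later. One route is an item that cannot be done for a physical reason after Baseline: it stays missing and has only Screening and Baseline values. If the line instead runs backwards through treated visits to fill Baseline, part of any treatment effect enters the baseline of those records and leaves their change score.

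**Working it through.** **Inputs.** Item maxima 10, 5, 5, 5, 5, 8, 12, 5, 5, 5, 5, summing to 70 (SAP 4.7.2). Baseline is Day 1 and 14 to 28 days after Screening (protocol 3.1, 7.2.1). Weeks 4, 13 and 26 are Days 28, 91 and 182. Visits are numbered 1 to 5 from Screening to Week 26 (protocol Table 3).

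**1. The SAP's example.** 70/55 = 1.27; 50 × 1.27 = 63.5 (63.64 without rounding the factor). Both give 64. The example reproduces, but a ceiling and rounding to nearest give the same answer here.

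**2. Rounding.** Shift = rounded value minus x, averaged over a grid of remaining-item sums S (equal weights, an assumption).
- ADAScog-11: x = S × 70/(70 − m), S = 10 to 50 in thirds (whole numbers if Word Recall is missing), attainable m = 5 to 20. Ceiling: 0.39 to 0.50. Nearest: 0.00 to 0.07.
- ADCS-ADL: x = S × 78/(78 − m), S = 20 to 70, m = 1 to 23. Ceiling: about 0.4 to 0.5. Nearest: between −0.02 and 0.09.

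**3. Line through Screening (S) and Baseline (B) only, read at Week 26.** Imputed value = B + k(B − S).
- Calendar days: k = (182 − 1)/gap. This is 181/21 = 8.6, with range 181/28 = 6.5 to 181/14 = 12.9.
- Visit numbers: k = (5 − 2)/(2 − 1) = 3.

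Take an item scored 0 to 5 in whole points and the smallest calendar factor, 6.5. A rise of 1 means B ≥ 1, so the line gives at least 1 + 6.5 = 7.5. A fall of 1 means B ≤ 4, so it gives at most 4 − 6.5 = −2.5. Any non-zero difference therefore ends at the limit. If S = B, the line is flat and the value is unchanged. On visit numbers, 0 then 1 gives 1 + 3 = 4, which is within range.

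**4. Missing Baseline item, if later visits enter the line.** Weight of visit i at Baseline: w = 1/n + (x0 − mean)(xi − mean)/Sxx.

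| Axis | Screening | Week 4 | Week 13 | Week 26 | Post-randomisation sum |
|---|---|---|---|---|---|
| Days, gap 21 | 0.524 | 0.378 | 0.187 | −0.089 | 0.476 (gap 14 to 28: 0.471 to 0.483) |
| Visit numbers | 0.571 | 0.286 | 0.143 | 0.000 | 0.429 |

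A constant 1-point drug effect on the item from Week 4 would move its Baseline value by 0.43 to 0.48 point. An effect growing in proportion to time to 1 point at Week 26 moves it far less on days (gap 21): 0.378 × 28/182 + 0.187 × 91/182 − 0.089 = 0.06.

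**5. Cases that neither rule covers.** One usable value in the whole study: no line can be fitted, and proration is barred because a value exists. An item first seen after the missing visit: there is no previous visit, and proration is again barred. CDR-SB and ADCS-ADL items missing at Baseline are exposed to this, as neither scale is given at Screening.

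**6. Trial level.** If 2 to 10% of ADAScog-11 totals are prorated (assumed; no figure is given), the ceiling moves an arm mean by 0.4 × 0.02 = 0.01 to 0.5 × 0.10 = 0.05, and this cancels if rates are equal across arms. The design difference is 2 points, with standard error 6 × √(2/143.2) = 0.71, where 143.2 = 179 × 0.8.

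**7. Word Recognition, side by side.** In protocol Appendix 1 item 7 "the subject is given one trial to learn a list of 12 words", and then 24 words are tested, of which the subject is told "Some of the words were on the list I just showed you and others are new". The SAP's note that "only reminders after the second word are included in the scoring range of 0-22" agrees with 24 test words (24 − 2 = 22). The protocol form labels its total in the same terms as the SAP. Neither document says what a *yes* to a new word scores.

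**The case against.** The SAP limits the exposure: it asks for every effort to recover missing items, imputes only below 30% missing, and scores cognitive inability at the maximum. The rounding phrase may mean ordinary rounding, and the only example fits that. The line is triggered by previous visits; for Baseline that means Screening alone, and the baseline definition is pre-dose, so nothing obliges a programmer to use treated visits. The calendar axis is an assumption too: SAP 4.7.2 codes week by visit number in the model, and on that axis the factor is 3.

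Most of this stands as a limit on size. It does not settle the rules. With Screening alone there is no line to fit and proration is barred, so the narrower reading leaves the Baseline case undefined. A factor that is 3 or 8.6 depending on an unstated axis is itself a gap.

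A reader might infer more, in three ways that the documents do not support:

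- *That Word Recognition is mis-scored*, since *yes* to all 24 words would literally score 0. The SAP repeats the protocol form, and Appendix 1 says "For specific instructions for all tasks, refer to the Administration Manual". That manual is not among the documents and may settle the rule.
- *That the Word Finding chart corrupts data.* Raters circle 0 to 5 on the protocol form, so a miscopied SAP chart changes no rater-entered score.
- *That the SAP fills Baseline from treated visits.* That is one of two readings.

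**Conclusion.** The concern holds for two stated rules in SAP 4.7.1.2. First, imputed ADAScog-11 and ADCS-ADL totals are rounded when observed totals and CDR-SB are not; on the ceiling reading that is a systematic 0.4 to 0.5 point per prorated total. Second, the line rule has no minimum, no named visits and no axis, and it crowds out proration. It can therefore extrapolate a 22-week-plus span from two visits 2 to 4 weeks apart, and it leaves some cases with no rule. Filling Baseline from treated visits is a possible reading that should be closed off: in affected records it would move part of any treatment effect into baseline.

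The expected effect on the treatment difference is small. It depends on how many assessments have some missing items, which the documents do not give, and for rounding on whether that rate differs between arms. The case for changing the text is that a programmer would otherwise have to choose between readings of a primary-endpoint rule with data in hand. The Word Finding and Word Recognition items are clarifications only.

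**What to change.** Before database lock, amend SAP 4.7.1.2:

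1. Leave imputed totals unrounded, as already done for CDR-SB.
2. Name the visits that enter the line and its time axis, and require at least two usable values.
3. Otherwise use the SAP's own proration. Use it also for a later visit when only Screening and Baseline are available.
4. Never use post-randomisation values for a Baseline item; use Screening or proration, and say which.

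In SAP 4.7.2, replace the Word Finding chart with the Appendix 1 item 10 anchors. Check in the Administration Manual how a *yes* to a new word is scored and how the maximum of 12 then applies, and state it.

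The cost is SAP wording and programming; SAP 4.11 allows changes up to lock. The sample size is unaffected. Only if the manual counts a *yes* to a new word, and the eCRF holds just a not-recalled total, would the worksheets' word-level answers have to be retrieved.

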8.9 Determination of Sample Size

A total of 537 subjects will be randomized into one of three treatment groups, SUVN-502 (50 mg), SUVN-502 (100 mg) or placebo (179 subjects per group). With a sample size of 537 subjects, there is at least 80% power to detect a 2-point drug-placebo difference on the ADAS-Cog with a standard deviation of 6, assuming a two-sided 5% significance level and a drop-out rate of 20% or less.

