4.4 Analysis Populations

Three populations are defined for the analyses:

- Modified intent to treat (mITT) population: All randomized subjects who receive at least 1 dose of study medication and have 1 post-baseline evaluation of the primary efficacy variable. Subjects will be assigned to the group they were randomized.
- Evaluable Population (EP): [REDACTED]
[REDACTED]
[REDACTED]
[REDACTED]
[REDACTED]
- Safety Population (SP): All randomized subjects who receive at least 1 dose of study medication. Subjects will be assigned to the treatment group based on the actual treatment received.

All efficacy analyses will be performed on the mITT population and the EP. The primary efficacy analysis of the primary endpoint will be based on the mITT population and a secondary analysis of the primary endpoint will also be performed based upon the EP. All secondary endpoints will be analyzed using both the mITT population and the EP.

Safety analyses will be performed on the SP. If a subject takes more than 1 study drug for any period of time, that subject will be included in the analyses with the highest dose group taken.

Demographic and baseline characteristics will be evaluated for the mITT population. Additional summaries will be presented using the Safety Population.

The number of subjects in the different analysis populations will be summarized by treatment group, and overall.

The subjects excluded from each analysis set will be listed with the reason for exclusion.

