4.10 Determination of Sample Size

A total of 537 subjects will be randomized into one of three treatment groups, SUVN-502 (50 mg), SUVN-502 (100 mg) or placebo (179 subjects per group). With a sample size

of 537, there is at least 80% power to detect a 2-point drug-placebo difference on the ADAScog-11 with a standard deviation of 6, assuming a 2-sided 5% significance level and a drop-out rate of 20% or less.

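### The SAP puts APO-E status into the primary MMRM with no level for an unknown genotype, so ungenotyped mITT subjects would drop out of the primary, secondary and pooled-dose analyses

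*SAP*

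**What the plan says.** - **Protocol model.** Protocol 8.5.1.2 specifies treatment, pooled site, week, treatment by week, baseline score and baseline by week. APO-E4 carrier status enters only the exploratory subgroup model in 8.5.1.3.
- **SAP model.** SAP 4.7.1.1 and 4.7.2 add APO-E status, age and baseline MMSE. APO-E has three categories: non-carrier, one allele, two alleles. The SAP commits to PROC MIXED code with the line "MODEL outcome = treat week treat*week base base*week apoe mmse_base age", and apoe is also in the CLASS statement. The baseline table in SAP 4.5.1 uses the same three categories.
- **Analysis set.** The primary analysis is on the mITT population, defined in SAP 4.4 as "All randomized subjects who receive at least 1 dose of study medication and have 1 post-baseline evaluation of the primary efficacy variable". A genotype is not required.
- **Missing data.** SAP 4.7.1.2 covers missing total scores and missing scale items. It does not mention a missing covariate.
- **Reuse of the model.** SAP 4.7.3 applies it to the secondary endpoints, SAP 4.7.1.6 to the pooled-dose comparison, and SAP 4.7.1.2 to the zLOCF sensitivity analysis.
- **Source of the genotype.** Protocol 6.4.2 and Table 3 schedule one blood sample at baseline. No criterion in Protocol 4.1 or 4.2 depends on the result.
- **Power.** SAP 4.10 claims "at least 80% power to detect a 2-point drug-placebo difference". Protocol 8.9 gives the inputs: a "2-point drug-placebo difference on the ADAS-Cog with a standard deviation of 6". Alpha there is 0.05, two-sided, and dropout is taken as no more than 20%.

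**The concern.** A record with no value for a model covariate has no row in the design matrix, so it cannot contribute to the fit unless the plan gives a rule. PROC MIXED by default leaves out any observation with a missing CLASS variable. Genotype is constant within a subject, so a sample that is not drawn, is lost or fails in the laboratory removes all of that subject's ADAS-Cog visits, not just one.

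The set actually analysed would be mITT subjects with a genotype, which the SAP neither names nor defines. The zLOCF analysis would not bring these subjects back, because it imputes scores and not genotypes. Without a written rule, the choice between dropping, recoding or imputing falls to whoever programs the analysis. If the gap is noticed only after unblinding, any choice is post hoc.

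**Working it through.** **1. Does any stated rule keep an ungenotyped subject?** Take a randomized subject who was dosed, has Week 4, 13 and 26 ADAS-Cog scores, and has no APO-E result. SAP 4.4 places this subject in mITT. SAP 4.7.1.2 does not apply, because no score or item is missing. In SAP 4.7.2 the subject belongs to none of the three APO-E categories, so the coded model uses none of the three visits. No readable rule intervenes.

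**2. Reproduce the plan's sample size.** Inputs from Protocol 8.9: difference 2, SD 6, two-sided alpha 0.05, power 80%, dropout 20%, 179 per arm. SAP 4.7.1.3 makes no multiplicity adjustment, so each dose is tested at 0.05.

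- Normal approximation: n = 2 × (1.960 + 0.842)² × 6² / 2² = 141.3, so 142 per arm. 142 / 0.8 = 177.5, so 178 per arm and 534 in total.
- t-test: 143 is the smallest whole n per arm that reaches 80% (142 gives 79.9%, 143 gives 80.2%). 143 / 0.8 = 178.75, so 179 per arm and 537 in total. This matches the plan.
- At 20% dropout, 179 × 0.8 = 143.2 per arm remain. Power is 80.3% (t) or 80.5% (normal).

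The stated figure is reproduced, with almost no slack.

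**3. Remove a share m for missing genotype.** m is an assumption. Evaluable n per arm = 143.2 × (1 − m). Power = P(|T| > t₀.₉₇₅), where T is noncentral t with 2n − 2 degrees of freedom and noncentrality 2 / (6 × √(2/n)).

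| m | Subjects of 537 | n per arm | Power (t) | Power (normal) |
|---|---|---|---|---|
| 0% | 0 | 143.2 | 80.3% | 80.5% |
| 1% | 5.4 | 141.8 | 79.9% | 80.1% |
| 2% | 10.7 | 140.3 | 79.5% | 79.7% |
| 5% | 26.9 | 136.0 | 78.2% | 78.5% |
| 10% | 53.7 | 128.9 | 76.0% | 76.3% |

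**4. How sensitive is this?** Power crosses 80% at 0.7% missing by the t-test (142.25 per arm needed; 1 − 142.25/143.2) and at 1.3% by the normal approximation (141.28 needed). A fall to 78% needs 5.5% (t) or 6.2% (normal) missing. With less dropout there is more room: by the t-test, 80% power survives 6.5% missing at 15% dropout and 11.7% at 10% dropout. If the covariates explained 5% of the residual variance (an assumption), the n needed would fall to 135.2, and 5.6% missing would be tolerable even at 20% dropout.

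**5. What an 'unknown' level does to the LS means.** By default LSMEANS weights the levels of a CLASS factor equally. With four APO-E levels, an 'unknown' level holding about 1% of subjects would take one quarter of the weight in each arm's mean. The difference between arms at a given week does not change, because the model has no treatment-by-APO-E term and the APO-E part cancels.

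**The case against.** The strongest case against the point is that little is at stake. The genotype sample is a scheduled baseline procedure for every subject, and the documents do not suggest that it will often fail. The calculation combines the worst dropout the plan allows, no overlap between dropouts and ungenotyped subjects, no contribution from dropouts' earlier visits, and no precision gain from the added covariates. This stands, and it is why the power figures are given only as a conditional range.

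A reader might infer four stronger things, none of which the documents support:

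- **That the planned 80% power is lost at about 1% missing.** The t-test figure does cross 80% near there, but only because the sample size was set to just reach it. The change is 0.4 points, and the normal approximation is still at 80.1%.
- **That the model contradicts the mITT definition.** SAP 4.4 defines a population; loss of records to a missing covariate arises in the model. This is an unstated rule whose default effect shrinks the declared set.
- **That subjects would vanish silently.** PROC MIXED reports the observations not used, and SAP 4.11 allows changes after blinded data review, before database lock. That route permits a rule but does not supply one.
- **That the treatment comparison would be biased.** The sample is scheduled at the baseline visit, and nothing in the documents links missing genotype to treatment arm.

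Redaction also limits certainty. The Evaluable Population definition, most of SAP 4.7.1.5 and the subset list in 4.7.2 are blacked out, so a genotype rule there cannot be excluded. The model description, code and missing-data section for the primary analysis are readable and contain none.

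**Conclusion.** The point holds as a gap in the primary analysis specification. The SAP adds a covariate that the protocol's primary model does not have, gives it no level for an unknown value, and commits to code that would exclude mITT subjects who lack it. The same exclusion carries into the secondary and pooled-dose analyses.

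The size depends on a missing rate that the documents do not give. With a difference of 2, SD 6, the full 20% dropout and no covariate gain, the t-test loss is about 0.4 points at 1% missing, about 2 points at 5% and about 4 points at 10%. The loss is therefore small unless several percent of genotypes are missing. The main reason to act is that the analysed set should be the declared one and the rule should be fixed before unblinding.

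**What to change.** Before database lock, amend SAP 4.7.1.1 and 4.7.2 as follows, with the same rule for every MMRM that reuses the model:

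- Code a missing genotype as a fourth APO-E level, 'unknown', so that every mITT subject stays in the analysis.
- Compute the LS means with observed-margin weights for APO-E, common to all arms, so that a sparse level does not distort the reported arm means. Request them by treatment and week, since the SAP text reports results by visit; week is then not averaged over, and the treatment contrast at each visit is unaffected by the weights.
- Report the number of subjects with unknown genotype in each arm.

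The cost is one extra model parameter, one line of data preparation and a sentence or two in the SAP. With all subjects kept, power stays at 80.3% (t) under the plan's own inputs at 20% dropout.
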